**Table 1 Schedule of Assessments**

	Day 0 Visit	12 Week Visit	26 Week Visit	52 Week Visit	Annual Visit	End of Study	Early Withdrawal Visit
	Window ≤45 Days from Last Dose a	±4 Weeks	±4 Weeks	±4 Weeks	±6 Weeks	4 (+1) Weeks from Last Dose	4 (+1) Weeks from Last Dose
Procedure							
Informed Consent	X						
Inclusion/Exclusion Criteria	X						
Medical History	X b						
Demographics	X c						
Physical Examination	X d			X	X	X o	X o
Weight	X Prior to Each Dose					X o	X o
mBMI e	X d			X	X	X o	X o
Height	X c						
FAP Stage and PND Score	X d			X	X	X o	X o
Karnofsky Performance Status	X						
NYHA Classification	X			X			[X] f
Vital Signs g	X Prior to Each Dose						
Safety Laboratory Assessments h	X d	X	X	X	X	X	X
INR	X						
Pregnancy Test (urine)	X i		X	X	X	X	X
C-SSRS Questionnaire			X	X	X	X	X

	Day 0 Visit	12 Week Visit	26 Week Visit	52 Week Visit	Annual Visit	End of Study	Early Withdrawal Visit
	Window	≤45 Days from Last Dose a	±4 Weeks	±4 Weeks	±4 Weeks	±6 Weeks	4 (+1) Weeks from Last Dose
Procedure							
TTR Protein (ELISA)	X d		X	X	X	X	X
TSH and Vitamin A				X	X	X o	X o
Blood Sample for Long-term Storage	X	X	X	X	X	X	X
mNIS+7 j	X d			X			[X] f
NIS+7 k	X d			X			[X] f
NIS only					X l	X m	X m
Grip Strength Test n	X d			X			[X] f
10-Meter Walk Test p	X d			X			[X] f
Ophthalmology Examination q	X d			X	X	X o	X o
Skin Punch Biopsy (IENFD and SGNFD) r				X	X	X o	X o
MR Neurography s ( Germany & France only )	X		X	X	X	X o	X o
Pharmacoeconomics Questionnaire	X			X	X	X o	X o
Norfolk QOL-DN t	X d			X	X	X o	X o
COMPASS 31 Questionnaire	X d			X			[X] f
R-ODS Disability	X d			X			[X] f
EQ-5D QOL	X d			X	X	X o	X o
Echocardiogram	X d,u			X			[X] f
Troponin I and NT-proBNP	X d			X			[X] f

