**Table 1 Footnotes:**

Abbreviations: C-SSRS = Columbia-Suicide Severity Rating Scale; COMPASS 31 = Composite Autonomic Symptom Score; ELISA = enzyme linked immunosorbent assay; EQ-5D QOL = EuroQOL; FAP = familial amyloidotic polyneuropathy; IENFD = intraepidermal nerve fiber density; mBMI = modified body mass index; mNIS = Modified Neuropathy Impairment Score; MR = magnetic resonance; NIS = Neuropathy Impairment Score; NT-proBNP = N-terminal prohormone of B-type natriuretic peptide; NYHA = New York Heart Association; PND = polyneuropathy disability; QOL-DN = Quality of Life-Diabetic Neuropathy; R-ODS = Rasch-built Overall Disability Scale; SGNFD = sweat gland nerve fiber density; TSH = thyroid stimulating hormone; TTR = transthyretin

- Every effort should be made to perform Day 0 visit 3 weeks (±3 days) from the last dose of study drug in the parent study. However, the Day 0 visit may occur within 45 days after the last dose in the parent study. Exceptions may be made for medical or regulatory considerations only after consultation with the Medical Monitor.
- Medical history includes TTR genotype. Ongoing AEs from the parent study will be captured as Medical History on the case report form (CRF). Similarly concomitant medications that continue from the parent study will be entered into the database.
- Assessment does not need to be repeated. Information will be obtained from parent study.
- Assessment/procedure does not need to be repeated if performed during the parent study within 45 days of first dose in this study.
- mBMI will be calculated within the clinical database; this calculation does not need to be performed at the study center.
- Assessment/procedure required only if patient withdraws before the 52-week visit.
- Vital signs include blood pressure, heart rate, body temperature, and respiratory rate. Collected supine using an automated instrument after patient rests for 10 minutes. Must be performed pre-dose.
- Includes serum chemistry, hematology, and urinalysis. Refer to Section 9.1.5 for specific laboratory assessments.
- Assessment does not need to be repeated if the patient had a negative pregnancy test (urine or serum) within 14 days of the first dose.

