### 3. INVESTIGATIONAL PLAN

#### 3.1. Overall Study Design

This is a multicenter, multinational, open-label extension study to evaluate the long-term safety and efficacy of patisiran in patients with FAP who have previously completed a patisiran study. Patients in this study will have completed “parent” study ALN-TTR02-003 or ALN-TTR02-004. Note that Study ALN-TTR02-003 is not being conducted in Japan.

Consented eligible patients will enroll in this study and receive 0.3 mg/kg patisiran IV once every 21 days for the duration of the study. All dosing visits have a window of  $\pm 3$  days. In order to maintain the every 21-day dosing schedule from the parent study, patients are expected to have their first visit (Day 0) on this study 3 weeks after their last dose visit on the parent study. However, if necessary, a patient may initiate dosing in this study up to 45 days from the time of the last dose in the parent study. Exceptions to this timing may be allowed for medical or regulatory considerations only after consultation with the Medical Monitor. The last testing visit in the parent study will serve as the baseline for this study, unless more than 45 days have elapsed, in which case the baseline tests will need to be repeated on Day 0. Eligibility for this study will be confirmed before administration of the first dose on Day 0.

The duration of the study has been determined to allow the collection of long-term safety, tolerability and efficacy data of patisiran in patients with FAP who have completed a prior study with patisiran. The estimated duration of the study is 5 years.

In order to reduce the potential for an IRR with patisiran, all patients on this study will receive premedications at least 60 minutes before the start of the patisiran infusion. Patisiran will be administered as a 70-minute IV infusion (approximately 1 mL/minute for the first 15-minutes followed by approximately 3 mL/minute for the remainder of the infusion). If the infusion duration for a patient was lengthened beyond 70 minutes due to the occurrence of an IRR while on the parent study, that infusion duration may be continued on this study for that particular patient. Returning the patient’s infusion duration to 70 minutes will require a discussion with the Medical Monitor.

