After the Day 0 visit, patients should return to the clinical site for patisiran dosing once every 21 ( $\pm 3$ ) days. Where applicable country and local regulations allow, patients may receive the patisiran infusions at home by a healthcare professional trained on the protocol and delivery of premedications and patisiran. Patients who are receiving patisiran infusions at home will have a phone contact with the site at least every 30 ( $\pm 5$ ) days. Patients will also have visits at the clinical site at approximately 12, 26 and 52 weeks, and yearly thereafter.

A complete set of efficacy assessments will be performed at 52 weeks, followed by more limited efficacy assessments yearly thereafter. In order to decrease the variability in the efficacy assessment testing at the 52-week visit, there will be a limited number of sites within any one territory that conduct these efficacy assessments (referred to as “Central Assessment Sites [CAS]”); these sites can dose and manage patients. There will also be sites that can dose and manage the patients (“Patient Care Sites [PCS]”), while sending the patients to the nearest CAS for their 52-week efficacy assessments. Every effort should be made for the patient to return to the same CAS center that the patient went to in the parent study. Yearly efficacy assessments

after the 52-week visit may be done at a PCS. Prior to starting the study, the CAS and PCS will create a delegation of responsibilities document that clearly details which site is responsible for which efficacy tests and safety parameters to ensure adherence to the protocol. This document will become part of the study site specific documentation.

Safety will be assessed throughout the study. Patients will return to the clinical site for safety evaluations at 12, 26 and 52 weeks during the first year and yearly thereafter. Patients will be continually assessed throughout the study for adverse events (AEs). Unscheduled visits for study assessments may occur if deemed necessary by the study personnel.

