### 4.4. Pregnancy and Breastfeeding Restrictions / Contraception Requirements

TTR transports vitamin A in plasma; therefore, reductions in circulating vitamin A levels accompany reductions in TTR caused by patisiran. Vitamin A deficiency has known effects on both male and female reproductive performance and embryo/fetal development. It is not known whether decreased levels of vitamin A at efficacious patisiran doses in ATTR patients who are male or who are women of child bearing potential will affect reproduction. Histopathological evaluations of all of the reproductive organs have been conducted in the rat and non-human primate (NHP) toxicology studies including a chronic NHP study in sexually mature animals, where there were no adverse effects in males (including sperm analyses and spermatogenic staging) or females. In a dose range-finding rat embryo/fetal development study

conducted with patisiran, there were no effects on mating, fertility, ovarian or uterine parameters, or fetal development despite reductions (-88% from baseline) in serum vitamin A in the dams dosed with the rat-specific TTR surrogate siRNA.

Women of child-bearing potential are defined as any woman or adolescent who has begun menstruation. A post-menopausal woman is defined as a woman who has 12 months of spontaneous amenorrhea or 6 months of spontaneous amenorrhea with serum FSH levels >40 mIU/mL or 6 weeks postsurgical bilateral oophorectomy with or without hysterectomy.

In this study, women of child-bearing potential must have a negative pregnancy test, cannot be breastfeeding, and must be using 2 highly effective methods of contraception prior to dosing on Day 0, throughout study participation, and for 75 days after last dose of patisiran in this study. Highly effective methods of birth control result in a low failure rate (ie, less than 1% per year). Acceptable forms of effective contraception are defined as follows:

- Hormonal: established use of oral, implantable, injectable, or transdermal hormonal methods of conception
- Placement of an intrauterine device (IUD)
- Placement of an intrauterine system (IUS)
- Mechanical/barrier method of contraception: condom or occlusive cap (diaphragm or cervical/vault cap) in conjunction with spermicide (foam, gel, film, cream or suppository)

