## 6.4.2. Study Drug Administration

Patisiran will be administered under the supervision of the site personnel every 21 ( $\pm$ 3) days. Patients who have received at least 3 doses of patisiran on this study at the clinical site with no evidence of IRRs or other adverse effects may have patisiran administered at home, where applicable country and local regulations allow. Home administration of patisiran will be done by a healthcare professional trained on the protocol and delivery of premedications and patisiran.

On all dosing days, patisiran will be administered as a 70-minute IV infusion (approximately 1 mL/minute for the first 15 minutes followed by approximately 3 mL/minute for the remainder of the infusion).

- If the patient experiences an IRR the infusion time may be extended up to 3 hours in the event of a mild or moderate IRR.
  - 1) If the patient experiences a mild or moderate IRR that resolves by slowing the infusion rate then no further premedication changes are recommended.
  - 2) If the patient experiences a severe IRR, then patisiran administration will not be resumed until the case is discussed with the Medical Monitor (see Section 6.4.3).
- If the infusion time for a patient was already extended on the parent study due to an IRR, that modified infusion duration may be continued on this study for that particular patient. Returning the patient's infusion duration to 70 minutes will require a discussion with the Medical Monitor.
- For the first 3 infusions of patisiran on this study, the patient's infusion site should be assessed for signs of any localized reaction during the infusion and for 30 minutes after the end of the infusion, and the patient will remain at the clinical site for 1 hour following completion of dosing.

If a patient does not receive a dose of patisiran within the dosing window ( $\pm$ 3 days), the dose will be considered missed and not administered.

Additional details can be found in the patisiran Pharmacy Manual.

In addition to study treatment, patients will receive the recommended daily allowance of vitamin A. Patients will receive this daily dose for the duration of their participation in the study while being administered patisiran. In Japan the clinical sites will provide the subjects with a prescription for vitamin A.

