#### **9.1.5.5. Pregnancy Screen**

Urine pregnancy tests are to be performed for all women of child-bearing potential. The timing of the tests is specified in [Table 1](#); additional testing may be done any time pregnancy is suspected.

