### **9.5.2. Pregnancy Reporting**

A female patient must have a negative pregnancy test within 14 days before the first dose of patisiran on this study. If a female patient is found to be pregnant during the course of the study or during the first month after receiving the last dose of patisiran, the Investigator should report the pregnancy to the CRO within 24 hours of being notified of the pregnancy. Details of the pregnancy will be recorded on the pregnancy reporting form. Treatment with patisiran will be discontinued in any patient who is found to be pregnant during the study. The patient should receive any necessary counseling regarding the risks of continuing the pregnancy and the possible effects on the fetus.

The pregnancy should be followed by the Investigator until completion. At the completion of the pregnancy, the Investigator will document the outcome of the pregnancy. If the outcome of the pregnancy meets the criteria for an SAE (ie, postpartum complication, spontaneous abortion, stillbirth, neonatal death, or congenital anomaly), then the Investigator should follow the procedures for reporting an SAE outlined above.

Pregnancy occurring in the partner of a patient participating in the study should also be reported to the Investigator, who will then report this to the CRO and follow to outcome as described above.

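### Pregnancy is a mandatory stop for patisiran, but scheduled pregnancy tests are up to 34 weeks apart in year one and nominally 52 weeks apart after Week 52, against dosing every 21 days

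*Protocol*

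**What the plan says.** **The stop.** Protocol Section 9.5.2: "Treatment with patisiran will be discontinued in any patient who is found to be pregnant during the study". The same section asks for a negative test within 14 days before the first dose in this study. A Table 1 footnote lets such a test replace the Day 0 test: "Assessment does not need to be repeated if the patient had a negative pregnancy test (urine or serum) within 14 days of the first dose".

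**The reason.** Section 4.4: "Vitamin A deficiency has known effects on both male and female reproductive performance and embryo/fetal development". It adds that the effect of the lower vitamin A levels seen at efficacious patisiran doses on reproduction is not known.

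**The tests.** The urine pregnancy-test row of Table 1 is marked at Day 0, Week 26, Week 52, the Annual Visit, End of Study and Early Withdrawal. It is blank at Week 12, and nothing ties a test to the dosing visits. Section 9.1.5.5 refers to Table 1 for the timing and adds that "additional testing may be done any time pregnancy is suspected".

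**The visits and doses.** Section 3.1: "Patients will also have visits at the clinical site at approximately 12, 26 and 52 weeks, and yearly thereafter". Section 6.4.2: "Patisiran will be administered under the supervision of the site personnel every 21" (±3) days. On length, Section 3.1 says: "The estimated duration of the study is 5 years".

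**The concern.** The stop acts only once a pregnancy is found, so it can work no faster than detection. For the first dose the protocol wants a test no more than 14 days old. For later doses the latest scheduled test may be half a year old in year one, and a year old or more after that. The protocol gives no reason for the difference.

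Two things are at stake. Dosing may continue in a pregnancy that the protocol says should end it. And a pregnancy that ends early and unrecognised between tests may never enter the pregnancy reporting of Section 9.5.2, so the record of exposed pregnancies could be incomplete.

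**Working it through.** The protocol states no figure on this point, so there is none to reproduce. The check compares the gap between consecutive scheduled tests with the dosing interval and with the length of a pregnancy.

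**Inputs from the protocol**
- Scheduled tests: Day 0, Week 26, Week 52, then yearly (Table 1; Section 3.1).
- Windows: ±4 weeks at Weeks 26 and 52, ±6 weeks at annual visits (Table 1).
- Dosing interval: 21 days, range 18 to 24 (Section 6.4.2).
- Duration: 5 years (Section 3.1), so about (5 × 52 − 52)/52 = 4 yearly intervals after Week 52.

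**Assumption, not in the documents:** pregnancy lasts 38 weeks from conception to 40 weeks from last menses.

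**Gaps between scheduled tests, and doses (weeks × 7 / 21)**

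| Interval | Nominal gap | Longest gap at the windows | Doses, nominal | Doses, longest |
|---|---|---|---|---|
| Day 0 to Week 26 | 26 wk | 26 + 4 = 30 wk | 8.7 | 10.0 |
| Week 26 to Week 52 | 26 wk | 26 + 4 + 4 = 34 wk | 8.7 | 11.3 |
| Week 52 to first annual visit | 52 wk | 52 + 4 + 6 = 62 wk | 17.3 | 20.7 |
| Annual to annual | 52 wk | 52 + 6 + 6 = 64 wk | 17.3 | 21.3 |

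If the Day 0 test is replaced by one taken 14 days earlier, the first gap is at most 30 + 2 = 32 weeks, still below 34. The shortest gaps after Week 52 are 52 − 4 − 6 = 42 weeks and 52 − 6 − 6 = 40 weeks.

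**Doses during one pregnancy**
- 38 weeks: 266/21 = 12.7 (266/24 = 11.1 to 266/18 = 14.8 across the ±3 days).
- 40 weeks: 280/21 = 13.3 (280/24 = 11.7 to 280/18 = 15.6).

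That is about 13 doses.

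**Does a whole pregnancy fit between two scheduled tests?**
- Year one: no. The widest gap is 34 weeks, below 38.
- After Week 52: yes at the nominal spacing, with 52 − 40 = 12 to 52 − 38 = 14 weeks to spare. At the shortest annual gap of 40 weeks, a 38-week pregnancy fits and a 40-week one only just equals it.

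**Does another provision close the gap?** The End of Study and Early Withdrawal tests do not shorten the interval for a patient who stays on treatment. Contraception is not detection. Testing on suspicion is permitted, not required. The phone contact for home-infusion patients (Table 1 footnotes) covers adverse events, concomitant medication and the infusion experience; no pregnancy test or question is named. No provision requires a test between scheduled visits.

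**The case against.** **There is no outright contradiction.** Section 9.5.2 applies to a patient found to be pregnant, Table 1 says when to look, and Section 9.1.5.5 allows a test at any time. All three can be followed together. This stands: the point is a mismatch between a mandatory stop and the schedule that supports it.

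**The safeguards are substantial.** Women of child-bearing potential must use two highly effective methods throughout, and Section 4.4 describes such methods as failing in less than 1% per year. Weight and vital signs are taken at every dose, patients are asked about changes in health, and home-infusion patients are phoned at least every 30 (±5) days. A term pregnancy unsuspected through about 13 doses would be unusual. This stands as to probability. It does not supply a required test.

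**Earlier detection protects only in part.** Section 1.2 reports that TTR returned to baseline only by Day 70 in the Phase 1 study, so stopping would not promptly reverse an effect already under way. Section 4.4 also reports no effect on fetal development in a dose range-finding rat study despite an 88% fall in serum vitamin A. Both temper the stake. Neither removes the protocol's own statement that the effect on reproduction is not known, nor its decision to stop treatment.

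**Stronger readings that the documents do not support**
- *A whole pregnancy could be missed at any time.* Only after Week 52; the year-one gaps are too short.
- *The stop cannot act in early pregnancy.* It can, whenever suspicion prompts a test.
- *Early losses are never detected.* A recognised loss can be reported by the patient, and Section 9.5.2 lists spontaneous abortion among outcomes to be handled as serious adverse events. Only unrecognised losses may be missed.
- *A planned result is biased.* Section 10.2.4 lists no pregnancy rate that an under-count would distort.

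**Conclusion.** The concern holds as a gap in the schedule. Scheduled tests are up to 34 weeks apart in year one (about 11 doses) and nominally 52 weeks apart after Week 52, 40 to 64 at the window limits, with about 17 doses at the nominal gap and 21 at the longest. In the worst case a whole pregnancy of about 13 doses falls between two scheduled tests after Week 52. The more realistic consequence is that a pregnancy is recognised, and the stop applied, some doses late.

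The whole-pregnancy figure rests on the assumed 38 to 40 weeks, on the pregnancy staying unsuspected and on no unscheduled test being done. The gap lengths rest on the protocol alone. The number of women of child-bearing potential is not given, so no expected count of exposed pregnancies can be derived. The timing is fixed in the protocol itself, since Section 9.1.5.5 points to Table 1; it is not a matter left to the statistical analysis plan.

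**What to change.** Reconcile the pregnancy-test row of Table 1 and Section 9.1.5.5 with the mandatory stop in Section 9.5.2 and the 21-day dosing, so that scheduled testing of women of child-bearing potential can support the stop.

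- **Week 12.** The safety laboratory assessments there already include urinalysis, so this is the obvious low-cost place to add a test.
- **After Week 52.** The sponsor should set and state the testing interval, including how it applies to patients infused at home, where local rules allow that. No interval is proposed here.
- **Unchanged.** The stop stays as written.

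The cost is test strips, a minor burden for patients and some data entry. For home infusions there is also a procedure for testing and for handling results, so that part is not free.

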## 10. STATISTICS

### 10.1. Sample Size

This is an open-label extension study enrolling patients who have previously completed a patisiran study; the size of the study is not determined via power analysis of particular hypotheses tests.

### 10.2. Statistical Methodology

Statistical analyses will be primarily descriptive in nature.

For categorical variables, summary tabulations of the number and percentage of patients within each category (with a category for missing data) will be presented. For continuous variables, the number of patients, mean, median, standard deviation, minimum, and maximum values will be presented.

All data will be provided in by-patient listings.

#### 10.2.1. Populations to be Analyzed

The following patient populations (ie, analysis sets) may be evaluated and used for presentation of the data:

- Full Analysis Set: All patients who were enrolled will be included in the full analysis set. The full analysis set will be the primary set for the analysis of efficacy data.
- Safety Analysis Set: All patients in the full analysis set who received patisiran. The safety analysis set will be used for the analysis of safety assessments.

